## Exclusion criteria:

1) Metastatic disease, or previous relapse

2) Age >70

3) Physical or mental handicaps that would impede to engage in moderate physical activity or participate in kitchen classes

Setting: The study will be carried out in collaboration by two institutes in Milan (the National Cancer Institute and the European Institute of Oncology), and one in Palermo (the Department of Oncology of the ARNAS-Civico Hospital).

### Recruitment

Potential participants will be recruited at the time of diagnosis or through follow-up clinics, patients' associations, or the media. Patients will be requested to sign an informed consent, including authorization for getting blood samples, for storing samples for future studies on the effect of diet on blood parameters, and on DNA polymorphisms that may modify the response to dietary changes, and for follow-up. We shall collect demographic information, measure body weight, height, waist circumference, and blood pressure, and take an early morning (0800-1000h) fasting blood sample to measure blood glucose, LDL and HDL cholesterol, triglycerides, testosterone and insulin. Eligible patients shall fill in a baseline questionnaire on medical history, medication use, reproductive and body weight history, usual physical activity (frequency, duration and intensity), and a validated semi-quantitative food frequency questionnaire.

**Biological bank**: Every about 12 month we shall collect and store at -80°C one aliquot of whole blood and three 2-ml serum aliquot. In a sample of cases we shall also preserve blood with RNAlater solution to allow the expression assay of several relevant genes.

### Randomization

We plan to recruit 1,200 high risk patients (400 per year) and to randomize them in two groups: 600 (control group) shall receive general standard written recommendation for healthy lifestyle without, however, any active support; 600 (intervention group) shall receive a combination of individual and group contacts over the course of one year, including kitchen courses, gym and dance classes, common meals and reinforcing meetings, with emphasis on a comprehensive dietary and life-style change.

Randomization will be carried out within strata of age, treatment group (no adjuvant therapy, chemotherapy only, hormonal therapy only, both hormonal and chemotherapy) and axillary nodal status at diagnosis. Allocation will be done centrally and blindly.

Patients not fulfilling the high-risk criteria will be given the same general recommendations as the control group, and will be followed up as an external low risk group.

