#### Follow-up and outcome events

The main outcome will be new BC events including: - new primary breast cancer

- local/regional recurrence
- distant/metastatic recurrence

The follow up will be based on the routine clinical follow-up at the collaborating hospitals, the periodic questionnaires to study participants, the regional cancer registry and hospital discharge diagnosis system, and death certificates

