### Statistical analysis

We shall first assess the baseline association between androgens, insulin, and several measures of adiposity including body mass index, waist circumference and (in a sample of cases) percentage body fat, with Spearman correlation coefficients. We shall then compare the change in food consumption, body weight, and geometric means of hormone end points from baseline to 12 months in the intervention and control group.

The main analysis of the intervention effect on the incidence of recurrences will be by intention to treat, i.e. based on assigned treatment at the time of randomization, regardless of adherence. As a secondary analysis we shall assess the effect by change in body weight and biomarkers. We shall compute total survival, disease free survival and relapse free survival.

Hazard ratios and confidence intervals will be computed by the Cox proportional hazard model, with standard clinical-pathological prognostic covariates as potential confounders. Separate analyses will be carried out by ER, PR and erbB2 status. Interim analyses will be carried out as soon as the total follow-up person-years reach 2,500 (corresponding to  $\alpha$  =0.10 and  $\beta$ = 0.20 for a 33% reduction of recurrence rate).

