# Feasibility

The principal investigator has long term experience in carrying on and coordinating epidemiological studies, including small-scale dietary intervention studies (22, 29, 30). The European Institute of Oncology has long term experience in chemoprevention studies. The Milan National Cancer Institute is fully equipped with facilities for kitchen courses, dedicated cafeteria, gym facilities. The Palermo oncology center has access to kitchen facilities in a nearby technical institute and has already carried out a dietary intervention study with very high compliance. The above institutions treat, respectively, about 3,000, 1,000 and 200 BC patients per year.

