### **Control of potential biases**

Selection bias: the randomization will be carried out blindly, without any possibility of changing the allocation, within strata of age, date of diagnosis, treatment allocation (depending on stage and hormone receptor status) and number of positive axillary nodes at diagnosis (none, 1-3, 3 or more). Performance bias: patients will be recruited after the main treatments have been planned or delivered. In no case the allocation to the intervention or control group or the compliance will affect treatment.

Measurement bias: patients and researchers cannot be blinded, but the ascertainment of outcome will be carried out by clinicians that are not involved in the study. Attrition bias: Based on previous studies we expect a fairly high compliance in the intervention

group (>90%) but also some modification in the control group. After the main analysis by intention to treat, therefore, secondary analyses will be carried out by compliance score. Milestones and timing:

 $1^{st}$ )

3rd Month:  $2^{nd}$ ) 12th Month: 16th 3rd) Month:

testosterone by 10% or more and serum glucose and insulin by 5% or more in at least 50% of participants.

Operative study protocol and information system

Recruitment of at least 300 patients in the first year.

Compliance evaluation. The aim is to decrease serum cholesterol and

4th) 24th Month: Test of follow-up procedures and comparison of observed and expected number of recurrences

5th) 35th Month: First outcome analysis

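### Centre is in neither list of randomisation strata nor in the analysis model; a centre term in the analysis is a free, small improvement, and no bias is at issue

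*Combined protocol and SAP*

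**What the plan says.** All references are to the combined protocol and SAP.

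- **Sites.** The Setting paragraph under Exclusion criteria says: "The study will be carried out in collaboration by two institutes in Milan", with a third in Palermo. Feasibility gives their size: "The above institutions treat, respectively, about 3,000, 1,000 and 200 BC patients per year".
- **Allocation.** Randomization: "Randomization will be carried out within strata of age, treatment group (no adjuvant therapy, chemotherapy only, hormonal therapy only, both hormonal and chemotherapy", followed by axillary nodal status. Control of potential biases gives a second list: "within strata of age, date of diagnosis, treatment allocation (depending on stage and hormone receptor status) and number of positive axillary nodes at diagnosis". The lists differ in date of diagnosis, but centre is in neither. The method is stated as "Allocation will be done centrally and blindly".
- **Analysis.** Statistical analysis has hazard ratios "computed by the Cox proportional hazard model, with standard clinical-pathological prognostic covariates as potential confounders". The comparison of 12-month change in food consumption, weight and hormones names no covariates. No centre-stratified model is planned.
- **Delivery.** The Intervention section relies on local group activities: kitchen courses for 15-20, shared meals for 50-60, monthly gymnastics. Feasibility describes a full set of facilities at the Milan National Cancer Institute, whereas "The Palermo oncology center has access to kitchen facilities in a nearby technical institute".
- **Detection.** Follow-up and outcome events: "The follow up will be based on the routine clinical follow-up at the collaborating hospitals", supplemented by questionnaires, the regional registry and discharge system, and death certificates.

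**The concern.** In a three-centre behavioural trial, centre can plausibly affect how well the intervention is delivered and how soon a recurrence is recorded. If centre is in neither the allocation nor the model, two things follow. The arms can differ by chance in centre mix, and variation between centres stays in the error term. A foreseeable question after the trial is whether one site shaped the result. Without a prespecified centre term, any answer is post hoc. At stake is a little precision and some robustness, not the validity of the test.

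**Working it through.** **1. The plan's own figure.** With a control risk of 30%, a 25% reduction (22.5%), two-sided alpha 0.05 and 80% power, the pooled two-proportion formula gives

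[1.96·√(2·0.2625·0.7375) + 0.8416·√(0.30·0.70 + 0.225·0.775)]² / 0.075² = 3.032 / 0.005625 = 539.1, that is 540 per arm.

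The continuity correction, (539.1/4)·[1 + √(1 + 4/(539.1·0.075))]² = 565.4, gives 566, as in the Statistical power table. The other seven cells reproduce in the same way. None contains a centre term.

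**2. Centre shares (assumption: accrual follows caseload).** 3,000, 1,000 and 200 of 4,200 are 71.4%, 23.8% and 4.8%. Palermo would supply 1,200·200/4,200 = 57 women.

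**3. Chance imbalance with 600 per arm, allocated without regard to centre.** For the largest centre's share, 1.96·√(0.714·0.286·2/600) = 0.051. The arms differ by no more than about 5 percentage points in 95% of trials (simulated: 5.2).

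**4. Resulting shift in the 5-year risk difference.** The documents give no centre-specific risks, so two patterns are assumed, both averaging 30%. With centre values at 0, d and 2d, the between-centre variance is

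d²·[(0.2381 + 4·0.0476) − (0.2381 + 2·0.0476)²] = 0.3175·d².

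- Risks 1:1.25:1.5 (27.7%, 34.6%, 41.5%; d = 0.0692): 1.96·√(0.3175·0.0692²·2/600) = 0.0044, or 0.4 points.
- Risks 1:1.5:2 (25.7%, 38.6%, 51.4%; d = 0.1286): 1.96·√(0.3175·0.1286²·2/600) = 0.0082, or 0.8 points.

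The planned difference is 7.5 points and the mean shift is zero. The shift is already part of the ordinary standard error of the unstratified comparison, √(2·0.2625·0.7375/600) = 2.5 points.

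**5. Type I error and power.** There were 40,000 simulated trials per cell, 600 per arm. A crude two-proportion test was compared with a Mantel-Haenszel test stratified by centre. The effect was an undiluted 25% reduction, without continuity correction.

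| Centre risks | Type I error, crude / stratified | Power, crude / stratified |
|---|---|---|
| equal | 5.13% / 5.06% | 84.19% / 84.19% |
| 1:1.25:1.5 | 5.04% / 5.01% | 83.99% / 84.12% |
| 1:1.5:2 | 4.83% / 4.81% | 84.02% / 84.55% |

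The gain is 0 to about 0.5 points.

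**6. 12-month change.** Let mean change differ between neighbouring centres by d within-centre SDs (assumed). Centre then explains 0.3175·d²/(1 + 0.3175·d²) of the variance.

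- d = 0.2: 0.0127/1.0127 = 1.3%.
- d = 0.5 (1.0 SD between extremes): 0.0794/1.0794 = 7.4%.

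Confidence intervals would narrow by 1 − √(1 − 0.013) = 0.6% to 1 − √(1 − 0.074) = 3.8%.

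**7. Cells if centre joins the strata.** Assume 2 age bands and 2 date bands, with the plan's 4 treatment groups and 3 nodal groups: 2·4·3·2 = 48 cells. With centre there are 144, or 1,200/144 = 8.3 women per cell on average. At Palermo it is 57/48 = 1.2.

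**The case against.** The strongest reply is that individual, central allocation makes every centre supply both arms. Centre is therefore balanced in expectation, and a hospital's surveillance practice applies to its intervention and control women alike. This stands. A reader might infer that centre differences bias the comparison. The documents do not support that: the mean shift is zero and the test keeps its size.

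Several further points also stand:

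- The documents give no event or detection rates by centre, so an effect of centre is plausible but assumed. Detection is only partly centre-based, because questionnaires and death certificates are not tied to a hospital.
- The 12-month analysis compares changes, which removes stable differences in level, and the Compliance section has serial testosterone and insulin samples assayed together. Only centre differences in change remain.
- Uneven delivery would modify the effect. A centre term neither equalises delivery nor tests for it.
- A reader might infer that chance allocation threatens the filling of courses at Palermo, where 21 to 36 of 57 women could fall in the intervention arm. But 57 over three recruitment years is 19 a year, or 9 to 10 in the intervention arm under perfect balance, still short of a group of 15-20. Low volume is the cause there, not allocation.
- Leaving centre out of already numerous allocation strata is a defensible choice.

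None of this supplies a reason to leave centre out of the analysis. The milestones foresee an operative protocol that might set allocation details, but nothing in the present text does so.

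**Conclusion.** The omission is real, holds under either list of strata, and is not cured elsewhere. Its consequence is small. There is no systematic bias and no inflation of type I error. Under 1 point of power for recurrence is at stake in the scenarios tried, and about 1% to 7% of the variance of 12-month change. These sizes rest on accrual in proportion to caseload and on assumed centre differences. The power figures also leave out the plan's allowance for imperfect compliance and contamination. This is a free improvement to the analysis, of minor severity. It does not show that the sample size or the randomisation is unsound, or that centre has to be a stratification factor.

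**What to change.** In the Statistical analysis section:

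1. Stratify the main Cox model by centre (three strata), keeping the planned clinical-pathological covariates.
2. Include centre as a fixed effect in the 12-month comparisons of weight, diet and hormones.
3. Define centre as the enrolling institute, fixed at randomisation, since some women will come through associations or the media.

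The cost is a few lines of text. The Cox strata add no parameters, and the 12-month models lose two degrees of freedom. The sample size is unchanged.

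Adding centre to the central allocation is optional. Because of the sparse cells it would need minimisation or fewer levels of another factor. It can be weighed when the two lists of strata are reconciled, which is needed in any case.

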#### Intervention

The intervention shall aim at increasing physical activity, controlling weight, and promoting healthy, low calorie diet.

a) Physical activity. The goals of the physical activity intervention are: - Achieve and maintain regular participation in a moderate intensity physical activity (approximately 3 to 5 METs) program of 210 minutes/week (30 min on average per day) over at least 3 days /week -Decrease sedentary behaviors by 30 minutes/day on at least 5 days/week. During the first 12 months one group physical activity session per month will be offered to enhance program adoption. Women who wish to take up vigorous sports will be encouraged to do so. For those who do not progress to more vigorous activity, the focus will be on maintaining moderate intensity activities, such as walking. For self-monitoring and compliance enhancement, study participants will use logs and fill-in questionnaires

b) Weight control. Reducing energy intake relative to expenditure is the primary dietary focus for promoting weight loss in overweight or obese participants, and maintaining a healthy energy balance is the primary focus for normal weight participants. Energy density of the diet has emerged as a dietary characteristic that can be easily manipulated to maintain volume and satiation despite reduced energy intake. Participants will be encouraged to include whole grains and high-fiber vegetables, which add bulk and volume to the meal, as major components of their diet, to choose cooked cereals rather than bread or dry crackers, eat a vegetable salad, vegetables or soup before eating higher energy foods, choose fresh fruit rather than juice, and plan the meals in order to limit the opportunities to wrestle with food choices, and to reduce overeating prior to the eating situation itself.

c) Healthy diet .In order to reduce glycemic and insulinemic response, recommendations will include:

- reducing calorie intake, through the preferred consumptions of highly satiating foods, such as unrefined cereals, legumes and vegetables.

- reducing high glycemic index food, such as refined flours, potatoes, white rice, corn flakes, and high insulinemic foods, such as sugar and milk, preferring instead whole grain rice, barley, millet, oat, spelt, quinoa and buckwheat, legumes (any type including traditional soy products), vegetables (any type, except potatoes)

reducing sources of saturated fat (red and processed meat, milk and dairy products) preferring instead unrefined vegetable fats, such as olive oil, nuts and oleaginous seeds.
reducing protein intake, mainly animal protein (except fish)

To reach these goals a multiple intervention strategy will be developed, based on the following: a) actions for both the intervention and the control group

- 1. invitation leaflet, explaining the rationale of the study and including basic life-style recommendations, based on the 1997 WCRF recommendations (to be updated in 2007) and the Italian National Institute of Nutrition food pyramid.
- 2. dissemination of the information on the study by media
- 3. yearly follow-up questionnaire on breast events and dietary and physical activity change

b) actions for the intervention group

- 4. Individual advice on diet
- 5. Individual advice on physical activity
- 6. Kitchen courses to teach basic Mediterranean and macrobiotic recipes (two 1-day course plus, ten 3-h courses associated with common dinner) (15-20 participants at a time)
- 7. Fortnightly common lunch or dinner (50-60 participant at a time)
- 8. Basic gymnastic course (twelve monthly- 2-hour courses)
- 9. Organization of "Solidal Buying Groups" in order to buy recommended food and other commonly used goods directly from the producers or from big retailers at a discounted rate.
- 10. Agreement with healthy food shops and organic farmers to obtain special price
- 11. Agreement with fitness centers, yoga or martial arts centers, and dance schools
- 12. Study newsletter, with scientific information, kitchen recipes, study facilities
- 13. DIANA-5 website and chat line to exchange recipes and experience
- 14. Periodic conferences on diet and health
- 15. Periodic reinforcement meetings with common meals, gymnastic sessions, and dancing, after the first year
- 16. Periodic body weight assessment (weekly self measurement and monthly measurement at the study center)
- 17. Discounted rate for advanced kitchen courses
- 18. Psychological support groups
- 19. Individual advise on the basis of the changes in body weight and blood parameters at follow-up examinations

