#### Insulin and related metabolic factors effect BC risk

Overweight and sedentary lifestyle are associated with insulin resistance. Women who gain weight in adulthood and overweight postmenopausal women have a greater risk for BC than lean women (11, 12). Postmenopausal women who engage in regular exercise (> 3 hours per week) have a reduced risk for BC compared with inactive women (13, 14). Several epidemiological studies found that high serum insulin and IGF-I levels are associated with increase BC risk (15-20), with, however, some inconsistencies as for the effect modification of age and menopausal status.

Insulin and testosterone effect prognosis in BC patients

In BC patients, high serum levels of insulin (21) and testosterone (22 and Micheli et al, submitted) are significantly associated with increased risk of recurrences; after adjustment for traditional prognostic factors (cancer stage at diagnosis, ER and PR) the RRs for BMI and for insulin in the upper quartile were about 2, while the RRs for testosterone in the upper tercile ranged from 2 to 7. We also found a borderline significant association of ER+ cancer with serum levels of estradiol, which, however, disappeared upon adjustment for testosterone levels (22). Testosterone levels are higher than estradiol levels, are easier to measure reproducibly and have lower intra- individual variability (23-25). For this reason, and because it proved to be predictive at any age, we chose testosterone as the main hormonal indicator of BC risk.

We also showed an high risk of recurrence in patients with metabolic syndrome, defined as the presence of three or more of the following factors: abdominal obesity (waist circumference >88 cm), hypertension (SBP>130 and /or DBP >85), hyperglycemia (>110mg/100ml), high triglycerides (>150 mg/100ml) or low HDL cholesterol (<50 mg/100ml) (26) (Table 1). Consistently, several observational studies suggested that sedentary habits (28) and overweight (27) are associated with increased BC incidence and BC recurrences.

Table 1. Hazard ratio of developing recurrences during 5.5-year follow-up of 110 BC patients according to the presence or absence of metabolic syndrome and serum testosterone levels above or under the median value (26).

Metabolic	Testosterone	Recurrence		Hazard	95% C.I
syndrome	>0.40 ng/ml	Yes	No	Ratio	
No	No	7	46	1	
Yes	No	1	3	2.2	0.2-19.4
No	Yes	17	24	3.8	1.5-9.5
Yes	Yes	7	5	6.7	2.3-19.8

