### Secondary aims include assessing:

- the effect of the combined dietary and physical activity change on the prevalence of metabolic syndrome and on biomarkers that are hypothesized to be intermediate factors in the association of diet and physical activity with BC

- the effect of the intervention on the development of other life-style related health conditions, such as other cancers, diabetes, hypertension and dyslipidemia, and on total mortality.

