### **Baseline and yearly measurements**

Height and weight: electronic scale with women in light clothes and without shoes. In a sample of cases body fat and lean mass will be measured with bioelectric impedance.

Blood pressure: electronic device.

Serum glucose, triglycerides and cholesterol: standard quality controlled laboratory techniques Serum Testosterone and Insulin: Radioimmunoassay (RIA). For testosterone we shall use a direct RIA kit which has been validated by comparison with indirect assay after organic extraction of serum samples and celite purification (44).

For a sample of patients, we plan to apply for further financial support to measure several other metabolic, endocrine and inflammation markers (estrogens, SHBG, IGF-I, IGFBP 1, 2 and 3, C-reactive protein, leptin and adiponectin) as well as the DNA polymorphism and RNA expression of several relevant gene, in collaboration with the Dept of Oncology of the Ospedale Civico ARNAS in Palermo and at the Institute of Endocrinology at the Milan University.

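### Metabolic syndrome, diabetes, hypertension and dyslipidemia are secondary outcomes, but no treatment clause and no follow-up medication data are specified, so women treated after randomisation can be misclassified

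*Combined protocol and SAP*

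**What the plan says.** The section on secondary aims lists "the effect of the combined dietary and physical activity change on the prevalence of metabolic syndrome" and, separately, the "development of other life-style related health conditions, such as other cancers, diabetes, hypertension and dyslipidemia, and on total mortality".

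The one definition of metabolic syndrome stands in the background section *Insulin and related metabolic factors effect BC risk*. It requires three or more of five components: a waist above 88 cm, and "hypertension (SBP>130 and /or DBP >85), hyperglycemia (>110mg/100ml), high triglycerides (>150 mg/100ml) or low HDL cholesterol (<50 mg/100ml". Every component is a measured value. Nothing is said about a woman whose value is normal because she takes a drug. *Identification of eligible patients* uses the term without redefining it.

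On data collection, *Recruitment* provides for a "baseline questionnaire on medical history, medication use, reproductive and body weight history", among other items. Item 3 of the action list in *Intervention*, which applies to both arms, is a "yearly follow-up questionnaire on breast events and dietary and physical activity change". *Baseline and yearly measurements* covers height, weight, blood pressure, glucose, triglycerides, cholesterol, testosterone and insulin. It lists neither drugs nor waist circumference. *Follow-up and outcome events* adds routine clinical follow-up, periodic questionnaires, the cancer registry, discharge diagnoses and death certificates, but the outcome it names is new breast cancer events.

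**The concern.** Drug treatment lowers the very values that define the syndrome. If the definition is applied as written, a woman who starts an antihypertensive, glucose-lowering or lipid drug and reaches a normal value loses that component. If she falls below three components, she counts as resolved although the condition has only been treated. The specified follow-up data would not allow this to be recognised or corrected.

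For diabetes, hypertension and dyslipidemia the gap is of another kind. No section says what makes an incident case, and no section names a source for new treatment. The sources listed under follow-up are described for breast cancer events and are likely to miss many conditions diagnosed and treated outside hospital.

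The plan already accepts the principle. *Compliance* recognises that adjuvant treatment may change the biomarkers and confound the comparison, and it aligns blood samples by treatment phase. It does not extend this to drugs for blood pressure, glucose or lipids.

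At stake is the between-arm comparison on these secondary outcomes.

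**Working it through.** The documents give no rate, sample size or power for these outcomes, so there is no stated figure to reproduce. The size below is an illustration.

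**Step 1: women with the syndrome per arm.** Table 1 (110 patients) gives the women eligible by testosterone or by the syndrome.
- Syndrome only: 1 + 3 = 4.
- High testosterone only: 17 + 24 = 41.
- Both: 7 + 5 = 12.
- Eligible: 4 + 41 + 12 = 57, of whom 4 + 12 = 16 have the syndrome; 16/57 = 28%.
- Per arm of 600: 600 × 16/57 ≈ 168.

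This is an upper-end figure, because women eligible by insulin alone enlarge the denominator only. Two assumed alternatives:
- A quarter of the remaining 53 women qualify by insulin: 57 + 13 = 70; 16/70 = 23%, about 137 per arm.
- A full quarter of all 110 are additional: 57 + 27.5 = 84.5; 16/84.5 = 19%, about 114 per arm.

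**Step 2: distortion.** Assumptions: start rates r_C (control) and r_I (intervention) among women with the syndrome; half of the starters fall below three components; without the drug they would still have the syndrome.

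Falsely resolved per arm = 168 × r × 0.5. Distortion = difference between arms, divided by 168 or by 600.

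| r_C vs r_I | Control | Intervention | Difference | Of 168 | Of 600 |
|---|---|---|---|---|---|
| 20% vs 10% | 16.8 | 8.4 | 8.4 | 5 points | 1.4 points |
| 30% vs 10% | 25.2 | 8.4 | 16.8 | 10 points | 2.8 points |
| 10% vs 20% | 8.4 | 16.8 | −8.4 | −5 points | −1.4 points |

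The first two rows hide benefit; the third creates apparent benefit. The 5 and 10 points do not depend on the count of 168. The whole-arm figures do: with 114 per arm they are 114 × 0.05/600 ≈ 1.0 and 114 × 0.10/600 = 1.9 points.

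**Step 3: direction and power under a harsher assumption.** Here the assumption is the share of all cases hidden by treatment, h, so that observed prevalence = true prevalence × (1 − h). If half of the starters drop below three components, h = 20% means that 40% start a drug. True prevalence is assumed to be 30% in control (15% of patients with the syndrome divided by the 50% selected, an upper-end value) and 22.5% in intervention.

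Power at n = 600 per arm, two-sided 0.05, is Φ[(|d|√n − 1.96√(2p̄(1 − p̄))) / √(p₁(1 − p₁) + p₂(1 − p₂))]. With nothing hidden: d√n = 0.075 × 24.495 = 1.837; 1.96 × 0.622 = 1.220; (1.837 − 1.220)/0.620 = 0.996; power 84%.

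| Hidden, control / intervention | Observed prevalence | Ratio | Power |
|---|---|---|---|
| 0 / 0 | 30.0% vs 22.5% | 0.75 | 84% |
| 30% / 30% | 21.0% vs 15.75% | 0.75 | 65% |
| 20% / 10% | 24.0% vs 20.25% | 0.84 | 35% |
| 30% / 10% | 21.0% vs 20.25% | 0.96 | 5% |
| 10% / 20% | 27.0% vs 18.0% | 0.67 | 96% |

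The last power is high only because the difference is inflated. With no true effect (30% in both arms), hiding 30% / 10% would show 21% vs 27%, a false disadvantage for the intervention.

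**Step 4: the three other conditions.** Without a case definition no misclassification rate can be calculated.

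**The case against.** Several stronger readings are tempting, and the documents do not support them.

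- *Follow-up records only measured values.* Not so. Routine clinical follow-up, periodic questionnaires and discharge diagnoses are also listed and may catch some cases.
- *Treated women are scored as free of diabetes, hypertension or dyslipidemia.* This is an inference. The cut-offs define syndrome components, not these diseases, so the provable defect is an undefined outcome with no stated source of treatment data.
- *The bias must run toward no difference.* That requires more drug starts in the control arm. Only the intervention arm has monthly weighing at the study center and individual advice based on blood results (items 16 and 19 of the *Intervention* list). That could lead to more detection and treatment in that arm, and so to an exaggerated benefit.
- *The loss is 5 or 10 points of prevalence.* Those points refer to women with the syndrome at baseline. For prevalence in the whole arm they become 1.4 or 2.8.
- *The data will never be collected.* Item 3 is one line in a list of actions, and an operative protocol is a third-month milestone. The defensible statement is that the data are not specified.
- *Development is meaningless for women who enter with the syndrome.* The word ordinarily implies new occurrence, and the syndrome itself is a prevalence aim. The at-risk group only needs to be stated.
- *Waist will not be re-measured.* *Compliance* expects it to fall relative to control, so repetition is evidently intended; it is simply missing from the list.

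What remains is a stated definition with no treatment clause, together with a stated questionnaire scope that leaves out drugs. Other follow-up sources do not change how that definition classifies a treated woman.

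**Conclusion.** The point holds, for secondary outcomes only. For metabolic syndrome, misclassification of women treated after randomisation follows directly from the definition, and the specified follow-up does not provide the data to correct it. For diabetes, hypertension and dyslipidemia, the outcomes lack a case definition and a reliable source for conditions treated outside hospital.

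On assumed start rates of 20% vs 10%, the distortion is about 5 points among women with the syndrome at baseline, or 1.4 points of the whole arm. At 30% vs 10% it is about 10 and 2.8 points. The start rates, and the half who drop below three components, are assumptions without a basis in the documents, and 168 women per arm is an upper-end count. The direction is unknown. The primary outcome and its sample size are unaffected.

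**What to change.** 1. Add to the yearly questionnaire, in both arms, new diagnoses of diabetes, hypertension and dyslipidemia, and the start or change of antihypertensive, glucose-lowering and lipid drugs.
2. For the secondary outcomes, count a condition or component as present if the measured value is abnormal or the woman is on drug treatment for it. Apply the same rule at baseline with the medication data already collected. Leave the eligibility criteria unchanged; the outcome fix does not need them to move.
3. State that development of each condition is analysed among women free of it at baseline, by value and by drug.
4. List waist circumference among the yearly measurements, since it is a syndrome component and is expected to change.

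The cost is a few questionnaire items, a sentence or two of definition, and a brief measurement at visits already planned. Drug history that is not collected prospectively is hard to recover reliably later, so the change should be made before follow-up begins or as early in it as possible.
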